8.2 Other Efficacy Analyses

No formal hypothesis testing will be done for the following exploratory objectives, but will be presented with descriptive statistical summaries, if applicable:

1. Summary results of the expression of human collagen VII as determined by immunofluorescence (IF) by treatment.
2. Summary results of the presence of anchoring fibrils as determined by immunoelectron microscopy (IEM) post-administration.

9 Safety and Tolerability

All safety analyses will be conducted in the Safety population. Safety measures include adverse events, physical examinations, vital signs and clinical laboratory tests.

9.1 Adverse Events

Verbatim descriptions of AEs will be coded using MedDRA, version to be delineated in the CSR. Summary tables will be provided for all treatment-emergent adverse events (TEAEs), but all AEs will be provided in a listing. A treatment-emergent AE is defined as any AE that newly appeared, increased in frequency, or worsened in severity on or after the initiation of active test article. An AE is considered treatment emergent if the AE start date and time is on or after the start date and time of the first administration treatment dose. If time of the AE is missing and it occurred on the same date as the first administration treatment dose, the AE will be defined as treatment emergent. If the start date of the AE is partial or missing and it cannot be determined if the AE occurred prior to or after the first administration treatment dose, the AE should be defined as treatment emergent.

An overall summary of AEs will include the number of subjects who experienced at least one AE of the following categories: any AE, any TEAE, any drug-related TEAE, any severe TEAE, any serious TEAE, any drug-related SAE, any serious TEAE leading to death, any TEAE leading to premature discontinuation

of treatment, any TEAE leading to premature discontinuation from the study, any TEAE leading to dose interruption of test article, and any serious TEAE leading to premature discontinuation of treatment dose.

The number and percentage of subjects reporting a TEAE in each treatment group will be tabulated by system organ class and preferred term; by system organ class, preferred term, and severity (mild, moderate, and severe); and by system organ class, preferred term, and relationship (unrelated or related to test article). The incidence of TEAEs will be summarized by preferred term, sorted by decreasing frequency in the KB103 group, for all TEAEs, related TEAEs, serious TEAEs, and TEAEs leading to study drug discontinuation. The number and percentage of subjects reporting a TEAE of wound site reaction (based on the MedDRA higher level term) will be tabulated by treatment group, preferred term and severity (mild, moderate, and severe). The incidence of serious TEAEs, and TEAEs leading to premature discontinuation of treatment by system organ class and preferred term. For all analyses of TEAEs, if the same AE (based on preferred term) is reported for the same subject more than once, the AE is counted only once for that preferred term and at the highest severity and strongest relationship to test article.

In addition, all AEs (including non-TEAEs), serious TEAEs, TEAEs leading to discontinuation of test article, and TEAEs leading to dose interruption of test article will be provided in listings by treatment group, study site, subject, verbatim term, MedDRA system organ class and preferred term, start and end date, seriousness flag, severity, relationship to test article, relationship to study protocol, action taken with test article, non-test article action taken and outcome.

Immune response adverse events due to a severe immune response determined by the Investigator to be possibly, probably or definitely related to KB103 will be summarized by the number and percentage reporting such AEs along with a subject listing.

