## 4 Study Design

### 4.1 Study Overview

This study is an intrasubject comparison of KB103-administered and placebo-administered wounds. Up to three 50 cm^2 areas will be selected for entry: one or two will be selected to receive topical KB103, and one to receive topical placebo.

The primary objective of this study is to evaluate clinical efficacy through digital imaging of wounds. Secondary objectives include an evaluation of change in an Investigator's global assessment and change in patient reported outcomes.

[figure not shown]
Patients will be administered Investigation Product (IP) in two cycles. Cycle 1 starts on Day 1. Up to three 50 cm^2 areas are administered IP (one or two KB103 and one placebo) every 2 to 3 days (to correspond with bandage changes) until wound closure, or up to 3 months. IP is administered to the entire areas, on the wound(s) and on intact skin.

Following this initial dosing period, patients will enter into an observation period in which wounds are monitored at home using a phone imaging app. Upon re-opening and/or expansion of a wound in the KB103 treatment area, patients will be asked to return to clinic or will be treated at home to begin the 2nd cycle of dosing.

The 2nd cycle mimics the first. The same 50 cm^2 areas are administered IP (one or two KB103 and one placebo) every 2 to 3 days until wound closure or up to 3 months. IP is administered to the entire areas, on the wound(s) and on intact skin.

After the 2nd cycle of IP administration, patients enter a second observation period. Patients image their wounds at home using a phone app, and return to the clinic at monthly intervals.

Time to wound closure and duration of wound closure will be evaluated after both the 1st and 2nd cycles. Safety will be monitored throughout the study.

Three additional new patients age 2 and older will be enrolled under this version. Patients from this protocol will be allowed to roll over into Phase 3 study of KB103.

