5.1.2 Safety Population

This population is defined as all subjects who were administered KB103.

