7.3 Treatment Compliance and Exposure

Exposure summary by treatment group will be presented for the Safety and PP populations. The distribution of subjects by the total number of weeks on therapy (baseline, 8, 10, and 12) will be presented. For the Safety population, the summary of exposure will be based on the actual treatment received.

Treatment compliance is defined as the number of wound treatment doses (KB103 and placebo) received divided by the number of doses expected, ($\times 100$) over the time period defined by the first and last treatment dose dates. Descriptive statistics for treatment compliance and the number and percentage of subjects at least 90% compliant will be presented by treatment group for the ITT, Safety, and PP populations.

8 Efficacy (Proof of Mechanism) Analyses

The study has a complete randomized-block design in which each subject serves as a block to receive all of the treatment conditions. The Phase I/II studies provided at least one pair of target wounds, with one wound being treated with placebo and one wound being treated with KB103. Efficacy measurements are taken multiple times (or repeatedly) over the on-treatment period and off-treatment period from each subject.

All data will be presented using summary statistics or frequency tables, as appropriate, and will be analyzed for superiority comparisons between KB103 and placebo treatments. The description of the sample will be done using summary statistics (n, mean, standard deviation, median, and maximum/minimum) for continuous data and using frequency statistics (counts and percentages) for categorical data. Hypothesis testing, unless otherwise indicated, will be performed at the 5% significance level (1-sided). All P-values will be rounded to four decimal places; P-values less than 0.0001 will be presented as '<0.0001' in all tables. Unless specifically stated, all confidence intervals will be two-sided with 95% coverage.

Efficacy measures collected pre-dosing will be considered as the baseline measurement (defined in [Section 6.2](#)) in this study. For all efficacy analyses, subjects will be analyzed in the group to which they were randomized.

The Sponsor, or their designee, will analyze the data using SAS® Statistical Analysis System Version 9.3 or higher.

8.1 Wound Efficacy Analyses:

8.1.1 Change in Wound Surface Area:

The efficacy analyses will be based on the observed ITT population.

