9.4 Laboratory Values

Laboratory data is collected during the study as outlined in the schedule of events ([Appendix 1: Schedule of Events](#)). Reference ranges are used to assess the laboratory data for clinical significance. Abnormal laboratory values which are unexpected or not explained by the subject's clinical condition should be repeated as feasible until confirmed, explained or resolved. Changes from baseline are recorded as an AE if deemed clinically significant by the Investigator or qualified designee.

The following evaluations are conducted:

Serum Chemistry / Metabolic Panel

- | | | | |
|------------------------------|-----------------|--------------------------------|-------------------|
| - Albumin | - AST (SGOT) | - Bilirubin, direct & indirect | - Globulin |
| - Alkaline Phosphatase Total | - Urea Nitrogen | - CO ₂ | - Potassium |
| - Anion Gap | - Calcium | - Creatinine | - Sodium |
| - ALT (SGPT) | - Chloride | - Glucose | - Total Bilirubin |
| | | | - Total Protein |

Hematology / Complete Blood Count with Differential

- | | | | |
|--------------|------------------|--------------------------|--------------------------|
| - WBC | - Platelet Count | - MCHC | - Monocytes, % and abs |
| - Hemoglobin | - MCV RDW | - Neutrophils, % and abs | - Eosinophils, % and abs |
| - Hematocrit | - RBC MCH | - Lymphocytes, % and abs | - Basophils, % and abs |

The absolute and change from baseline laboratory data from the above evaluations will be summarized by treatment and evaluation timepoint. Baseline is defined as the lab value closest to and prior to the first dose of either treatment.

Detailed subject listings of all laboratory data collected during the study will be provided. Laboratory values outside normal limits will be identified in the subject data listings with flags for low (L) and high (H).

Data from the following other laboratory evaluations will be provided in subject listings:

- Urine and Pregnancy Test Results
- HSV Antibody Assay
- Collagen VII Antibody Assay
- Viral Shedding

10 Other Relevant Data Analyses/Summaries

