10.1 Protocol Deviations

A listing of all protocol deviations will be provided. Deviations will also be reviewed by the Sponsor and categorized into general categories such as major and minor. Review of protocol deviations will be conducted and finalized prior to analyzing the database. The number of subjects with at least one protocol deviation, the number of subjects with a minor protocol deviation, the number of subjects with a major protocol deviation, and the number of subjects with at least one major deviation in each category will be presented by treatment group for the ITT population. A major deviation is defined as one that potentially affects the efficacy and/or safety analyses.

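### Systemic adverse events, blood results, systemic medications and subject-level deviations are split by treatment although every subject receives both, and wound-site reactions are counted by subject rather than by wound

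*SAP*

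**What the plan says.** **Design.** Protocol 4.1 states: "This study is an intrasubject comparison of KB103-administered and placebo-administered wounds". SAP section 8 describes a block design in which "each subject serves as a block to receive all of the treatment conditions". Protocol 6.5 ties placebo dosing to the days on which KB103 is given. SAP 5.1.2 defines the Safety population: "This population is defined as all subjects who were administered KB103". SAP section 9 runs all safety analyses in that population.

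**Output ordered by treatment.**
- Adverse events, SAP 9.1: "The number and percentage of subjects reporting a TEAE in each treatment group will be tabulated by system organ class and preferred term". Incidence tables are sorted by frequency in the KB103 group. Wound-site reactions have their own table, also as subject counts by treatment group. A repeated preferred term counts once per subject.
- Chemistry and haematology, SAP 9.4: absolute and change-from-baseline "laboratory data from the above evaluations will be summarized by treatment and evaluation timepoint".
- Deviations, SAP 10.1: "the number of subjects with at least one major deviation in each category will be presented by treatment group for the ITT population".
- Prior and concomitant medications, SAP 10.3: summarised and listed by treatment.

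**Output with no stated treatment split.** The overall adverse event summary (SAP 9.1), vital signs (9.2), physical examinations (9.3), severe immune-response events (one number and percentage, 9.1), and the antibody and viral shedding results (subject listings, 9.4).

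**The concern.** A systemic event, a blood value, a systemic medicine or a subject-level deviation such as a missed visit has no wound treatment. Nobody in the Safety population received placebo alone. Because placebo accompanies KB103 on dosing days, timing cannot separate the two either. The SAP gives no rule for placing such an item in one column or the other. Whoever programs the table must invent one, and that choice fixes the result.

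At stake is how the safety tables of a Phase I/II gene-therapy vector will be read. Two columns headed KB103 and placebo look like controlled evidence. For subject-level data they are either one set of numbers printed twice or a set of causality judgements laid out as if they were a control group.

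The wound-site table has a different problem. It can be interpreted, but its unit of counting favours placebo, because most subjects offer two KB103 wounds for a reaction to occur on and only one placebo wound.

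**Working it through.** The documents give no safety figure to reproduce. The check has three parts.

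**1. Is there an attribution rule?** None was found in any place that could hold one.
- The treatment-emergent definition (SAP 9.1) sets only a start time.
- The adverse event attributes in Protocol 9.1.1 and 9.4 cover description, dates, severity, relationship, action and outcome. No wound identifier is named.
- Protocol 9.3 sets relatedness against anesthesia, device and injection procedure, not KB103 against placebo.
- SAP 10.3 separates prior from concomitant medication by the first KB103 application only.

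**2. Subject-level event under different rules.** Assume an event in x = 3 subjects. The documents' subject counts differ: 11 when the overview table in SAP section 3 is summed for v1.0 to v3.2, 12 in the SAP text, and up to 14 in the Protocol synopsis. All three are shown.

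| N | Counted under every treatment received | Counted under KB103 only |
|---|---|---|
| 11 | 3/11 = 27.3% vs 27.3% | 27.3% vs 0% |
| 12 | 3/12 = 25.0% vs 25.0% | 25.0% vs 0% |
| 14 | 3/14 = 21.4% vs 21.4% | 21.4% vs 0% |

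Mixed judgement gives values in between. With N = 12, one event under both columns and two under KB103 only gives 25.0% vs 1/12 = 8.3%. The same three events therefore yield a difference of anything from 0 to 25 percentage points. For laboratory values, each subject has one result per timepoint. If every subject enters both columns, the columns are identical and the difference is 0 by construction.

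**3. Wound-site reactions counted by subject.** Wounds per subject come from the SAP section 3 table:
- v1.0: 2 subjects, 1 KB103 and 1 placebo wound each.
- v2.2: 4 subjects, 2 and 1.
- v3.1/v3.2: 5 subjects, 2 and 1.
- KB103 wounds: 2×1 + 4×2 + 5×2 = 20. Placebo wounds: 2 + 4 + 5 = 11.
- Adding 3 subjects under v4.0 (one or two KB103 areas each, Protocol 4.1) gives 23 to 26 KB103 and 14 placebo wounds.

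Assume the same reaction risk p on every wound, independent between wounds, so there is no treatment effect. A subject with two KB103 wounds shows at least one KB103 reaction with probability 1 − (1 − p)², against p for the single placebo wound. Over the 11 subjects of v1.0 to v3.2, the expected KB103 rate is [2p + 9(1 − (1 − p)²)]/11.

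| p | KB103 rate, 2:1 subject | KB103 rate, all 11 subjects | Placebo rate |
|---|---|---|---|
| 5% | 9.75% | 8.9% | 5% |
| 10% | 19% | 17.4% | 10% |
| 20% | 36% | 33.1% | 20% |
| 30% | 51% | 47.2% | 30% |

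For p = 10%: 1 − 0.9² = 0.19, and (2×0.10 + 9×0.19)/11 = 1.91/11 = 0.174. Independence matters. If a subject's two KB103 wounds always reacted together, the 2:1 rate would be 10%, equal to placebo. With correlation between zero and perfect, the rate lies between 10% and 19%. A per-wound denominator removes this bias under either assumption.

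**The case against.** The strongest reply is that this is descriptive reporting in a pilot study and that no placebo-controlled safety claim is planned. The safety objectives in SAP 2.1 concern events associated with KB103 and changes in laboratory values, vital signs and examination, with no comparator. SAP section 9 states no safety hypothesis test. Events are also tabulated by relationship and listed by subject, so with about a dozen subjects a reader can check each one. Protocol 10.6 asks for no by-treatment safety table.

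These points are correct and limit the harm. They do not supply an attribution rule, and relationship to test article is an investigator's causality opinion, not a control.

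Three stronger readings are tempting and are not supported:
- **That the whole safety comparison is meaningless.** Wound-site reactions have their own table, and Protocol 9.4.1 has both wounds of a pair monitored, so local tolerability can be compared within subject. Several other summaries carry no treatment split at all.
- **That the tables will make KB103 look no worse than placebo.** A zero difference follows only from double counting, which the SAP does not prescribe. Assigning events to KB103 alone, or counting wound reactions by subject, works against KB103. The direction is not fixed.
- **That there is no placebo safety information, or that all deviations and medications belong to the person.** Each subject is meant to have a placebo wound, so a placebo wound denominator exists. Doses are counted per wound treatment (SAP 7.3), so a missed application can be wound-specific, and Protocol 4.3 deals with therapy applied to individual wounds. Such items may properly be shown by wound treatment.

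**Conclusion.** The point holds for subject-level data in SAP 9.1, 9.4, 10.1 and 10.3. There the KB103-placebo contrast carries no information: it is exactly 0 under double counting and otherwise whatever the assigning judgement makes it (0 to 25 percentage points in the 3-of-12 illustration). This follows from the design and does not depend on sample size.

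For wound-site reactions the plan is under-specified but can be interpreted once repaired. Counting subjects gives KB103 a spurious excess of up to 9 percentage points in a 2:1 subject at an assumed 10% per-wound risk. That figure rests on equal risk and independence between wounds, and it shrinks to 0 as reactions on the same person become fully correlated.

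The plan should be changed before the tables are produced. The efficacy analyses are unaffected.

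**What to change.** 1. In SAP 9.1, 9.4, 10.1 and 10.3, report systemic adverse events, laboratory values, systemic medications and subject-level deviations in one all-subjects column. This matches what SAP 9.2 and 9.3 already do for vital signs and examinations.
2. Tabulate by wound treatment only wound-site events, wound-specific deviations and topical treatments applied to a study wound. Use wounds as the denominator (20 KB103 and 11 placebo planned for v1.0 to v3.2) and show the number of subjects alongside.
3. State the rule that assigns an event to a wound, and apply the count-once rule within each wound treatment. Otherwise a reaction on both a KB103 and a placebo wound collapses into one entry.

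**Cost.** Revised table shells and a short SAP amendment, with no new visits or assessments. If the case report form did not record wound location, local events will have to be assigned to wounds from source documents or verbatim terms. That is modest work at this sample size but more than reformatting. SAP section 1 says that a partial analysis has already been done, so any by-treatment safety tables from it should be reissued in the same layout.

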2.2.2 Other

- 1) To evaluate the expression of human collagen VII as determined by immunofluorescence (IF)
- 2) To evaluate the presence of anchoring fibrils as determined by immunoelectron microscopy (IEM) post-administration

3 Overview

The Phase I/II studies were randomized placebo controlled intrasubject comparison of KB103-administered and placebo-administered wounds.

To date, KB103 has been administered to 12 patients enrolled onto 4 versions of the Phase I/II protocol. A summary of the protocols and patients enrolled are presented below.

Phase	Protocol:	SN and Date:	# of pts	Wound size	# of wounds treated	Dose	Dosing days
1	v1.0, 19Apr2018	SN0001, 4/20/2018	2, Pts 01-02 Adults	Up to 10cm ²	2: one KB103, one placebo	1e8 PFU/wound/day	0, 2, 14, 28, 30
Following v1.0, the protocol was amended to increase the frequency and PFU level of the doses, and to administer to patients age 5 and older.							
2a	v2.2, 08Oct2018	SN0008, 10/09/2018	4, Pts 03-06 2 adults, 2 children age 13&14	Up to 20 cm ²	3: two KB103, one placebo	3e8 PFU/wound/day with the option to escalate to 6e8 PFU/wound/day	1, 2, 3, 4, 5, 30, 60, 90
Following 2.2, the protocol was amended to administer KB103 every two to three days to correspond with bandage changes. The potential number of doses increased, and the dose level was set at 2e8 PFU/wound/administration.							
2b	v3.1, 12Mar2019 and v3.2*, 25Jun2019	SN0016, 3/4/2019	5, Pts 07-11 3 adults, 2 children age 14&15	Up to 20 cm ²	3: two KB103, one placebo	2e8 PFU/wound/day	Every 2 to 3 days up to 15 per month
Following 3.2, the protocol was amended to administer KB103 in 2 cycles. The age of inclusion was reduced to 2 years old. Wound areas increase to up to 50cm ² , and with the increase in area the dose was increased to 6e8 PFU per area.							
2c	v4.0, 01Aug2019	SN0024, 8/5/2019	3, TBD	Up to 50 cm ²	Up to 3; 2 KB103 and one placebo	6e8 PFU/wound/day	Every 2 to 3 days until wound closure x 2 cycles

*v3.2 clarified the long-term follow-up

4 Study Implementation

Detailed information for the protocol study visits, is provided in the sections below and in the Schedule of Events ([Appendix 1: Schedule of Events](#)).

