11.1.3 Protocol Version 3.1

Visit	1			2	3	4		
Day	0/Screen/BL ¹	1	3	15	30	60 ²	90	91-180 ³
Genetic Testing	X							
Bacterial Culture ⁴	X	X		X	X	X	X	X
Urine Pregnancy Test ³	X	X				X		
HIV, Hep B, Hep C Testing ³	X	X				X		
Hematology & Chemistry ⁵	X				X		X	X
COL7 Antibody Assay ⁴	X				X		X	
HSV Antibody Assay ⁶	X				X		X	
Wound Assignment	X							
Pre-dose tattoos	X							
Concomitant Medications		X	X	X	X	X	X	X
Adverse Events		X	X	X	X	X	X	X
Viral shedding (skin swab)	X	X	X	X	X	X	X	X
Physical Exam	X						X	
PRO Assessment	X				X	X	X	X
Global Wound Assessment	X				X	X	X	X
Vital Signs	X				X	X	X	X
At-home wound imaging ⁷							X	
On-site wound imaging	X	X	X	X	X	X	X	
At-home topical IP administration							X	
On-site topical IP Administration					X	X	X	X
ID KB103 admin to intact skin ⁸					X			
Intact skin biopsy ⁹					X	X	X ⁹	X
Wound biopsy ¹⁰	X				X	X	X	X
X	Optional procedures. Early results may negate the need for ID injection and biopsies to intact skin in later patients.							

¹ Diagnostic screening procedures can be performed prior to the visit as indicated below

² Day 15 and 60 visits are required for patients that receive ID injections to intact skin at Day 1.

³ Follow-up visits after Day 90 are conducted as the subject is able at the discretion of the Investigator

⁴ Conducted as clinically indicated

⁵ After screening/baseline, performed only as clinically indicated to minimize blood draws

⁶ May be waived after the first follow-up visit if prior results are negative.

⁷ Subjects will be instructed to image the target wounds during bandage changes (approximately twice per week). ⁸ Optional ID administration for subjects at least 13 years old. Performed at the discretion of the Investigator. Early results may negate the need for ID injection and biopsies to intact skin in later patients.

⁹ Two intact skin locations will be biopsied on Day 30

¹⁰ Biopsies are performed at the discretion of the Investigator and Sponsor.

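### SAP 9.1 counts wound site reactions per subject, but most subjects have two KB103 wounds and one placebo wound, so equal risk per wound would not give equal percentages

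*SAP*

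**What the plan says.** **Unit of counting.** SAP 9.1 says that the count and percentage of "subjects reporting a TEAE of wound site reaction (based on the MedDRA higher level term) will be tabulated by treatment group", broken down further by preferred term and severity. For all treatment-emergent tables, "if the same AE (based on preferred term) is reported for the same subject more than once, the AE is counted only once".

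**Design.** SAP section 8 states that "each subject serves as a block to receive all of the treatment conditions". The Safety population in SAP 5.1.2 follows from KB103 exposure: "This population is defined as all subjects who were administered KB103". The same people therefore stand behind both columns.

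**Wounds per subject.** SAP section 3 states: "To date, KB103 has been administered to 12 patients enrolled onto 4 versions of the Phase I/II protocol". Its table gives subjects 01–02 (v1.0) one wound on each treatment. For subjects 03–06 (v2.2) and 07–11 (v3.1/3.2) the entry is "3: two KB103, one placebo". Under v4.0 there may be up to two KB103 areas and one placebo area; Protocol section 6 says one or two KB103 areas.

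**Other KB103 sites.** Protocol 1.5 records that v1.0 KB103 was given both topically and intradermally. The v3.1 schedule in SAP 11.1.3 carries the footnote "Optional ID administration for subjects at least 13 years old".

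**Not found.** The SAP has no adverse event rate per wound and no adjustment for the number of wounds. It gives no rule for assigning a reaction to a wound or a treatment, and the listing fields in 9.1 include no wound identifier.

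**The concern.** A subject-level percentage is the usual safety summary when each subject receives one treatment. Here each subject receives both, and in most subjects KB103 has twice as many sites as placebo. A subject with two KB103 wounds enters the KB103 numerator if either wound reacts, but enters the placebo numerator only if the single placebo wound reacts. The denominator is one subject in each column.

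At stake is how the table is read. If the KB103 percentage is higher, the reader cannot tell poorer local tolerability from the 2:1 allocation. If the percentages are similar, the reader cannot tell that KB103 may be better tolerated per wound. The problem affects reactions that have been assigned correctly to a wound, so better attribution alone would not remove it.

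**Working it through.** The documents give no wound-reaction rate or ratio, so there is no stated figure to reproduce. The check is what the planned table would show if KB103 and placebo had the same risk per wound.

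**Inputs from SAP section 3**

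- Subjects treated: 12. By version: 2 (v1.0), 4 (v2.2), 5 (v3.1/3.2). This implies 12 − (2 + 4 + 5) = 1 under v4.0.
- Subjects with two KB103 wounds: 4 + 5 = 9, or 10 if the implied v4.0 subject has two KB103 areas.
- f = 9/12 = 0.75, or 10/12 = 0.83.

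**Assumptions not in the documents**

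- p, the risk of a reaction per wound, the same on both treatments: 0.05 to 0.30.
- ρ, the correlation between a subject's two KB103 wounds: 0 to 0.5 as the main range, with 0.8 and 1 also shown.
- Each reaction is assigned to the treatment of the wound where it occurs.

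**Formula**

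- P(both KB103 wounds react) = p² + ρp(1−p).
- P(at least one reacts) = 2p − p² − ρp(1−p) = p + p(1−p)(1−ρ).
- KB103 subject percentage = (1−f)p + f[p + p(1−p)(1−ρ)] = p + f·p(1−p)(1−ρ).
- Placebo subject percentage = p.
- Ratio = 1 + f(1−p)(1−ρ).

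**Ratio, from f = 0.75 to f = 0.83**

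| p | ρ = 0 | ρ = 0.5 | ρ = 0.8 | ρ = 1 |
|---|---|---|---|---|
| 0.05 | 1.71–1.79 | 1.36–1.40 | 1.14–1.16 | 1.00 |
| 0.10 | 1.68–1.75 | 1.34–1.38 | 1.14–1.15 | 1.00 |
| 0.20 | 1.60–1.67 | 1.30–1.33 | 1.12–1.13 | 1.00 |
| 0.30 | 1.53–1.58 | 1.26–1.29 | 1.10–1.12 | 1.00 |

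**Size in subjects.** The expected gap is 12·f·p(1−p)(1−ρ), which is 9p(1−p)(1−ρ) at f = 0.75.

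- p = 0.10, ρ = 0: 9 × 0.09 = 0.8 of a subject (2.0 against 1.2).
- p = 0.20, ρ = 0: 9 × 0.16 = 1.4 subjects (3.8 against 2.4, or 32.0% against 20.0%).
- At ρ = 0.5 these gaps halve to 0.4 and 0.7.

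**Per-wound denominators.** There are 9 × 2 + 3 × 1 = 21 KB103 wounds or areas (22 if the v4.0 subject has two) and 12 on placebo. The expected rate is p in each column, so the ratio is 1.00 for every p and ρ.

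**The case against.** The strongest reply is that this is a descriptive table in about 12 people. SAP 9.1 tabulates and plans no adverse event test. All events are also listed by treatment group and subject, and SAP section 3 states the 2:1 allocation openly, so a careful reader can look at the cases one by one. The stopping criteria in Protocol Table 1 count events and do not use this table. The distortion runs against KB103, so it does not conceal harm. All of this stands, and it limits the weight of the point. It does not remove it: the listing has no wound identifier, so a reader may be unable to rebuild a per-wound rate from it.

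The size can also be challenged. Wounds in one person share disease, skin and dressing method, so ρ could be well above 0.5, and at ρ = 1 the effect disappears. Protocol 1.5.3 and 1.6 report no KB103-related adverse events in the first six subjects. That does not fix p, but it gives no support for high reaction rates. At low p the ratio is larger while the gap in subjects is smaller.

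Three stronger readings are tempting and are not supported.

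- A reader might infer that KB103 will look worse by a known factor. Neither p nor ρ is in the documents, so any factor is conditional.
- A reader might take this as the only within-subject comparison of local safety. Protocol 9.4.1 requires treated and paired wounds to be watched for blistering and border expansion, and the general tables in SAP 9.1 by treatment group would carry other local events.
- A reader might add the intradermal sites to the imbalance. In v3.1 that dosing was optional and to intact skin, and nothing says such events would fall under the wound site reaction term.

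**Conclusion.** The point holds as a conditional one. Under equal risk per wound, the planned subject percentages favour placebo whenever ρ and p are below 1. The expected ratio is about 1.26 to 1.79 for assumed p of 0.05 to 0.30 and assumed ρ of 0 to 0.5, about 1.1 to 1.2 at ρ = 0.8, and 1.00 at ρ = 1. The share f rests on the SAP's count of 12 treated subjects and on the inference that the twelfth came in under v4.0.

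In absolute terms the effect is roughly one subject. The direction is certain only if reactions are assigned by wound. The SAP does not say so, and its count-once rule leaves open how a subject with reactions on both treatments is shown. The flaw is modest, but its direction can be predicted, and it should be corrected before the table is produced.

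**What to change.** In SAP 9.1:

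- Tabulate wound site reactions per treated target wound, and per treated area under v4.0, because Protocol 6.3 lets one area hold several wounds and intact skin. The numerator is wounds or areas with at least one event; the denominator is the number treated with KB103 or with placebo. Apply the count-once rule within wound or area.
- State that a reaction is assigned to the wound or area where it occurs, and add that identifier to the AE listing.
- If the subject-level percentage is kept, footnote that it is not comparable between treatments because of the 2:1 allocation.
- List any reactions at intradermal KB103 sites separately.

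The cost is SAP wording, one table shell and one listing field, plus some data work. A split by treatment needs only KB103 or placebo, whereas a per-wound count needs to know which of two KB103 wounds reacted, so some AE records may need a query. Wounds within a subject are correlated, so the per-wound rates should be presented as descriptive.
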